---

## STATEMENT OF COMPLIANCE

The trial will be carried out in accordance with the International Conference on Harmonisation Good Clinical Practice (ICH GCP) and the following:

- United States (US) Code of Federal Regulations (CFR) applicable to clinical studies (45 CFR Part 46, 21 CFR Part 50, 21 CFR Part 312, and/or CFR Part 812)

National Institutes of Health (NIH)-funded investigators and clinical trial site staff who are responsible for the conduct, management, or oversight of NIH-funded clinical trials have completed Human Subjects Protection and ICH GCP Training.

The protocol, informed consent form(s), recruitment materials, and all participant materials will be submitted to the Institutional Review Board (IRB) for review and approval. Approval of both the protocol and consent form must be obtained before any participant is enrolled. Any amendment to the protocol will require review and approval by the IRB before the changes are implemented to the study. In addition, all changes to the consent form will be IRB-approved; a determination will be made regarding whether a new consent needs to be obtained from participants who provided consent; using a previously approved consent form.

## 1 PROTOCOL SUMMARY

### 1.1 SYNOPSIS

**Title:** MKit: A Pilot Study Testing a Life Skills Application to Address Interpersonal Relationships in College

**Study Description:** This study will conduct a second pilot test of the MKit web-based application (WebApp). MKit was previously adapted to a diverse (race, ethnicity, gender/sexual identity) college population with a focus on life skills and holistic self-care as reinforcement to currently available primary prevention programming available to freshman students. Our hypothesis is that the adapted WebApp will be safe, acceptable, and students will be willing to use it as a reinforcement to current university primary prevention programming.

**Objectives:**

- Primary: To evaluate the safety, usability, acceptability, and willingness of using the adapted WebApp among a randomized sample of 300 first year university students.
- Secondary: To complete preliminary evaluations on retention and efficacy measures such as sexual and intimate partner violence knowledge, attitudes, and experiences (victimization and perpetration) to allow for power calculations for a future R-level submission.

**Endpoints:**

- Primary: Safety (qualitative interviews), Usability (System Usability Scale, Brooke, 1986), Acceptability (investigator generated), and willingness to use (qualitative interviews).
- Secondary: Retention (percent completing follow-up surveys), Sexual and Intimate Partner Violence Knowledge (adapted from Texas Education Program Participant Response Form), Self-Efficacy of Protective Behaviors Related to Sexual and Intimate Partner Violence (investigator generated), Intimate Partner Violence Attitude Scale (adapted from Finchman, Cuit, Braithwaite, & Pasley, 2008), Consensual Sexual Activity (investigator generated), Sexual victimization/perpetration (Sexual Experiences Survey, Koss et al., 2007), and Universal Violence Prevention Screening (adapted from Heron, Thompson, Jackson, & Kaslow, 2003).

**Study Population:** 300 first year university students (150 Control Group, 150 Intervention Group)

[figure not shown]
**Phase:** Pilot

**Description of  
Sites/Facilities  
Enrolling  
Participants:**

University of Michigan Residence Halls (Alice Lloyd and Couzens)

Description of Study Intervention:	Web-based app that uses a life skills approach to address healthy relationships and sexual violence.
Study Duration:	2 years 9 months
Participant Duration:	For pilot study – 6 months

## 1.2 SCHEMA

## 1.3 SCHEDULE OF ACTIVITIES (SOA)

Procedures	Preparation before recruitment	Baseline	1-month follow-up	5-month follow-up	Post-study semi-structured interviews
Randomization by residence hall	X				
Demographics		X	X	X	
Sexual and Intimate Partner Violence Knowledge		X	X	X	
Self-Efficacy of Protective Behaviors Related to Sexual and Intimate Partner Violence		X	X	X	
Intimate Partner Violence Attitude Scale		X	X	X	
Consensual Sexual Activity		X	X	X	
Sexual Experiences Survey (Victimization and Perpetration)		X	X	X	
Universal Violence Prevention Screening		X	X	X	
System Usability Scale			X	X	
System Acceptability			X	X	
User Data			X	X	
Reaction to content					X
Perceived safety					X
Desirability					X
Willingness for future use					X

## 2 INTRODUCTION

### 2.1 STUDY RATIONALE

There have been minimal attempts at providing reinforcement for students around the primary prevention of sexual violence and nobody has approached this topic with the consideration of holistic well-being in mind. Many of the currently available primary prevention programs include a one-time interaction and do not provide reinforcement throughout the student's college career (Banyard, Moynihan, & Plante, 2007; Foshee et al., 2004; Moynihan et al., 2015; Taylor, Mumford, & Stein, 2015; Taylor, Mumford, Stein, & Woods, 2015). Principles of learning suggest that attitude change and skill training are more effective with reinforcement (Skinner, 1958). There is a need for holistic interventions that provide students with the means to address all of the physical, emotional, and social changes they may be experiencing during their transition to young adulthood. Past research has emphasized that life skills and social competency are promising approaches that address individuals within their ecological context (Krug, Mercy, Dahlberg, & Zwi, 2002).

### 2.2 BACKGROUND

With a national annual incidence rate of 5%, rape is the most frequent violent crime that occurs on college campuses (Finn, 1995; Fisher, Cullen, & Turner, 2000). Nearly 80-90% of college students know the perpetrator, which increases the likelihood that the rape will be completed, rather than attempted (Fisher et al., 2000; Karjane, Fisher, & Cullen, 2005). Furthermore, many college survivors do not perceive or acknowledge their experiences as a rape, often because of lack of evidence, the absence of a weapon, or because alcohol and/or drugs were involved (Fisher, Daigle, Cullen, & Turner, 2003; Karjane et al., 2005). These characteristics of sexual assault in college therefore contribute to the underestimation, under reporting, under prosecution, and low rates of seeking post-assault services among college survivors (BonDurant, 2001; Karjane et al., 2005).

Despite the high prevalence of rape in the United States, an event with long-term negative effects on a survivor's health, few survivors receive comprehensive post-assault care. In the period immediately following a rape, about half of all survivors will have evidence of physical trauma, up to 30% contract a sexually transmitted infection (STI), and 5% of female survivors become pregnant (Resnick et al., 2000). Specific to college survivors, about 20% report physical injuries (Fisher et al., 2000), many fear social consequences so they alienate themselves from campus activities or drop out of school, and it appears that college women who experience post-traumatic stress disorder (PTSD) from an assault may use substances and/or sexual behavior to reduce distress (Messman-Moore, Ward, & Brown, 2009). Post-assault, survivors can access comprehensive health services through referral by rape crisis centers or via the emergency department from specially trained sexual assault nurse examiner (SANE) programs. Comprehensive care includes 1) treatment of physical injuries or other sequelae of the assault, 2) pregnancy prevention, including options if emergency contraception is not effective, 3) STI screening and treatment, 4) psychological care for PTSD, 5) forensic and victim services, and 6) legal care, including safety from the perpetrator and the ability to report the assault and press

charges if the survivor desires (Tjaden & Thoennes, 2006). However, only one in five women raped as an adult reported their rape to the police and of these reported rapes, prosecution rates were only 37% (Tjaden & Thoennes, 2006). Thus, the prevalence of rape is under reported, under prosecuted, and many women do not seek care after experiencing rape due to multiple barriers to care (Munro, 2014).

Even with the high prevalence and severe physical health, mental health, and social outcomes associated with sexual violence, there are limited data available on effective primary prevention programs (Centers for Disease Control, 2016). A recent systematic review of primary prevention programs for sexual violence identified only three primary prevention strategies that have demonstrated significant effects on sexual violence, including *Safe Dates*, *Shifting Boundaries*, and the 1994 Violence Against Women Act (VAWA) Funding (DeGue et al., 2014). However, there are promising trends that favor multisectoral programs that engage stakeholders to challenge the acceptability of violence and the underlying social risk factors. There is strong consensus among researchers that more rigorous evaluation of promising programs is needed in order to continue to address sexual violence (Ellsberg et al., 2015).

Furthermore, recent national legislation has also highlighted the need for primary prevention of sexual violence. The *Dear Colleague Letter* issued by the Obama Administration in 2011 recommended that institutions of higher education implement preventive education programs focused on sexual violence for incoming students. The 2014 VAWA prescribed more specific recommendations that new students and employees must be offered primary prevention and awareness programs focused on domestic violence, sexual assault, stalking, and rape. The 2014 VAWA acknowledged specific content that should be included in these programs but did not stipulate how these programs were to be administered to incoming students. Thus, each institute of higher education implements primary prevention programming individually, often using a combination of web-based, in-person, and performance-based methods.

Many college campuses rely on online learning modules to meet the requirements of the 2014 VAWA; however, there is a lack of evidence on the effectiveness of these programs and the potential that mobile or web-based applications hold for the prevention of sexual violence. Technology has become a ubiquitous modality for communication and accessing knowledge across the United States. In 2011 the White House called for initiatives that leveraged technology to prevent dating and sexual violence (Rosenthal, 2013). This resulted in the creation of a mobile application called *Circle of 6* (<http://www.circleof6app.com/>), which makes it easy to contact a person in your circle to let them know where you are and what you need. More recently, a randomized controlled trial at a university in the Southeastern United States found a web-based bystander intervention approach, *RealConsent*, significantly reduced sexual violence perpetration and increased knowledge around consent, intervening, and rape myths and decreased negative attitudes around hostility toward women (Salazar, Vivolo-Kantor, Hardin, & Berkowitz, 2014). However, neither of these technology-based approaches targets the social and cultural constructions of sexual violence that promote gender inequality and discrimination nor do they offer holistic approaches to primary and secondary prevention (Dartnall & Jewkes, 2013).

A holistic approach recognizes college students as individuals transitioning into young adulthood. The transition into young adulthood is associated with myriad of preventable health problems including higher rates of mortality and more involvement in health risk behaviors (Ozer et al., 2012). Additionally, college students are often learning to manage school, work, new relationships, stress, conflict, and their own health for the first time as independent young

adults. A holistic approach aims to identify the student's goals and needs by increasing their ability to make decisions based on their personal values while also addressing communication skills in interpersonal relationships as an upstream approach to reduce sexual violence in the campus community. Positive and respectful communication within interpersonal relationships may help prevent some types of unwanted sexual activity. Furthermore, when students make decisions consistent with their values, they may be less likely to engage in behaviors or encounter situations where sexual assault perpetration or victimization could occur.

## 2.3 RISK/BENEFIT ASSESSMENT

### 2.3.1 KNOWN POTENTIAL RISKS

There is no more than minimal risk to the study subjects. There is a rare risk that a participant may experience emotional discomfort related to survey or semi-structured interview questions. All participants will receive resources to help alleviate any potential discomfort and will have the opportunity to skip any questions they choose. The rare possibility of breach of confidentiality exists. All data will be stored on a secure, HIPAA-compliant server and drive with monitored and controlled access to reduce this risk.

### 2.3.2 KNOWN POTENTIAL BENEFITS

The study participants will have the direct benefit of receiving information through a holistic, life-skills approach to addressing interpersonal relationships and sexual violence. This content may help them to navigate their own relationships.

### 2.3.3 ASSESSMENT OF POTENTIAL RISKS AND BENEFITS

The minimal risks associated with this study are reasonable given the potential impact of the project. The results of this study will provide the basis to scale-up this innovative intervention to reach a high-risk and vulnerable group, as college females are among those at the highest risk for sexual violence. This study therefore provides the opportunity to develop a low-cost/high-impact reinforcement intervention that could improve interpersonal relationships and reduce sexual violence within college campuses. As such, the available information suggests that the present clinical study has an acceptable risk-benefit ratio.

## 3 OBJECTIVES AND ENDPOINTS

Objectives	Endpoints	Justification for Endpoints
Primary		
To evaluate the safety, usability, acceptability, and willingness of using the adapted WebApp among a randomized sample	Safety will be assessed through qualitative interviews  Usability will be measured through the System Usability Scale (Brooke, 1986)	The endpoints are common outcomes of interest for studies of technological interventions. These outcomes will be measured throughout

of 300 first year university students.	
Acceptability will be measured through an investigator generated scale
 
Willingness to use will be assessed through qualitative interviews
	
the study, to observe changes overtime with continued exposure to the intervention. These endpoints are important outcomes, as interventions must be safe, acceptable, and usable to ensure broad scale uptake.


Secondary
 
To complete preliminary evaluations on retention and efficacy measures, such as sexual and intimate partner violence knowledge, attitudes, and experiences (victimization and perpetration) to allow for power calculations for a future R-level submission.
	
Retention will be measured as the percentage of participants completing the 1- and 5-month follow-up surveys.
 
Sexual and Intimate Partner Violence Knowledge will be measured with 20 items adapted from the Texas Education Program Participant Response Form (https://www.wcasa.org/file_open.php?id=787).
 
Confidence in the ability to handle situations related to sexual and intimate partner violence will be measured using 15 investigator created items that called the, Self-Efficacy of Protective Behaviors Related to Sexual and Intimate Partner Violence.
 
Attitudes related to Intimate Partner Violence Attitude Scale will be measured using 34 items adapted from Finchman, Cuit, Braithwaite, & Pasley (2008).
 
Consensual Sexual Activity will be measured with 2 primary questions developed by the investigators.
 
Sexual victimization (n=10) and perpetration (n=10) will be measured with the Sexual Experiences Survey (Koss et al., 2007).
 
Experiences of intimate partner violence will be measured with 26 items adapted from the Universal Violence Prevention Screening (Heron, Thompson, Jackson, & Kaslow, 2003).
	
The endpoints are important, as the WebApp under study is a primary sexual violence prevention intervention with a focus on healthy relationships. As such, knowledge, attitudes, and experiences of sexual and intimate partner violence victimization and perpetration are outcomes of interest. Though this pilot study is not powered to detect changes in these secondary outcomes, obtaining data for power calculations for a larger study is a key component of this study.

## 4 STUDY DESIGN

### 4.1 OVERALL DESIGN

This project builds on the current momentum to address the primary prevention of sexual violence within United States institutions of higher education as well as the proliferation of web-based applications. A before-and-after quasi-experimental, mixed-method pilot design will be used to gather acceptability and safety data as well efficacy trends. Two residence halls (Alice Lloyd and Couzens) at the University of Michigan will be randomized to receive either: (1) the control arm (n=150) which will receive usual care only (all incoming students receive three programs about healthy relationships and sexual violence including Haven, Relationship Remix, and Change it Up) or (2) the usual care (n=150) described above and the web-based intervention (MKit). We will use cluster-randomization by residence hall (to minimize contamination associated with individual-level randomization of students living in the same residence hall). Following the informed consent process, students in both conditions will complete a baseline survey of xx questions. Baseline measures will include: 1) demographic data (n=12), 2) investigator developed questions on knowledge about sexual and intimate partner violence (n=20) adapted from the Texas Education Program Participant Response Form ([https://www.wcasa.org/file\\_open.php?id=787](https://www.wcasa.org/file_open.php?id=787)), 3) investigator developed questions on self-efficacy (n=15), 4) 34 questions from the Revised Intimate Partner Violence Attitude Scale (Finchman, Cuit, Braithwaite, & Pasley, 2008), 5) investigator developed questions on consensual sex (n=2), 6) 10 items from the Sexual Experiences Survey (SES) will measure past experiences with sexual violence (Koss et al., 2007) and 10 items from the Sexual Experiences Survey (SES) will measure past experiences with perpetration (Koss et al., 2007), and 7) 26 questions from the Universal Violence Prevention Screening Protocol – Adapted questions (Heron, Thompson, Jackson, & Kaslow, 2003). All of these are measures have been validated and used extensively in the United States to measure knowledge and attitudes related to gender-based violence. Following the survey, students in the Intervention group will be given the opportunity to interact with the application at their own pace, choosing which content to view in the order they prefer.

The Control group will only receive the usual care delivered to all incoming University of Michigan students, which includes Haven (an online course about sexual violence), Relationship Remix (an interactive program about healthy relationships and sexual violence delivered by peers), and Change it Up (a theater based performance on bystander intervention). The Intervention group will receive the usual care described above as well as access to MKit. They will be encouraged to interact with MKit throughout the study. Data will be collected on the content viewed by the participants, as well as the amount of time they spend within each content area, and the order in which they view the content.

At 1 and 5 months, we will repeat all baseline measures in both groups. Participants in the Intervention group will also be asked to complete the 10-item System Usability Scale (Brooke, 1996) and an investigator created 5-item acceptability scale.

Post-intervention semi-structured interviews will be conducted with 25 participants, including 15 participants from the intervention group and 10 participants from the control group, to assess perceived safety, reaction to content, desirability, willingness to continue using the content, and willingness to recommend the content to others. Prior to commencing the interviews, we will ask each participant to complete a paper demographic survey.

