#### 4.3 JUSTIFICATION FOR DOSE

Intervention group participants will have five months to interact with MKit content, as this time period should present sufficient time for meaningful short-term change in the outcomes of interest. Further, the study will run for the duration of the school year, allowing study staff to follow students from the beginning of the school year to the end of the school year as they interact with MKit.

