## 8 STUDY ASSESSMENTS AND PROCEDURES

### 8.1 EFFICACY ASSESSMENTS

The efficacy of this study is not a primary outcome as this is a pilot study focused on safety, acceptability, usability, and willingness to use. However, a number of measures will be used to gather preliminary data for future scale-up at all three time points (baseline, 1-month, and 5-months). Study participants' knowledge, attitudes, and experiences will be measured with the following measures:

- 1) Investigator developed questions on knowledge about sexual and intimate partner violence (n=20) adapted from the Texas Education Program Participant Response Form ([https://www.wcasa.org/file\\_open.php?id=787](https://www.wcasa.org/file_open.php?id=787))
- 2) Investigator developed questions on self-efficacy (n=15)
- 3) 34 questions from the Revised Intimate Partner Violence Attitude Scale (Finchman, Cuit, Braithwaite, & Pasley, 2008)
- 4) Investigator developed questions on consensual sex (n=2)

- 5) 10 items from the Sexual Experiences Survey (SES) will measure past experiences with sexual violence (Koss et al., 2007) and 10 items from the Sexual Experiences Survey (SES) will measure past experiences with perpetration (Koss et al., 2007)
- 6) 26 questions from the Universal Violence Prevention Screening Protocol – Adapted questions (Heron, Thompson, Jackson, & Kaslow, 2003).

All of these are measures have been validated and used extensively in the United States to measure knowledge and attitudes related to gender based violence.

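### No look-back is set for the violence-experience items at 1 and 5 months, so as written the follow-up scores can mix events before MKit access with events after it

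*Combined protocol and SAP*

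**What the plan says.** Section 4.1 describes the perpetration measure thus: "10 items from the Sexual Experiences Survey (SES) will measure past experiences with perpetration". Section 8.1, which covers all three time points, describes the victimization measure in the same way: "10 items from the Sexual Experiences Survey (SES) will measure past experiences with sexual violence". For partner violence, the Section 3 table says: "Experiences of intimate partner violence will be measured with 26 items adapted from the Universal Violence Prevention Screening". None of these gives a start point or a recall window.

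On repetition, Section 4.1 says: "At 1 and 5 months, we will repeat all baseline measures in both groups". Section 8.1 agrees: "a number of measures will be used to gather preliminary data for future scale-up at all three time points". The schedule of activities (1.3) lists the same instruments at baseline, 1 month and 5 months without a window.

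On exposure, access to MKit comes after baseline: "Following the survey, students in the Intervention group will be given the opportunity to interact with the application at their own pace". Section 4.3 justifies the five months of access on the ground that "this time period should present sufficient time for meaningful short-term change in the outcomes of interest".

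On analysis, Section 9.4.3 plans descriptive statistics and an ANOVA of scores by arm. It has no new-event outcome and no rule for events already reported at baseline. Sections 9.4.1, 9.4.3 and 9.4.9 say that the direction of effects will be examined to support later power calculations. Section 4.2 treats supplying data for those calculations as central to the pilot.

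**The concern.** MKit can only influence events that happen after a student gains access. An item about past experiences, asked again at 1 and 5 months, also collects events from before that point. Those events occur in both arms whatever MKit does, so they pull the ratio between arms toward 1. They also raise the reported proportion above the risk that belongs to the five-month window.

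The stake is the use to which the data will be put. A later trial that counts new events, but takes its control rate from these surveys, could be sized on the wrong quantity. The two kinds of event cannot be fully separated once the surveys are closed. Baseline answers identify students with an earlier event, but under an open-ended frame a repeat event in such a student cannot be recognised, and no such derivation is planned.

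**Working it through.** The plan gives no event rate, effect size or power figure for these outcomes (9.2 says that no calculation was made), so there is nothing to reproduce. What follows is an illustration.

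**Inputs from the documents.** Five months of access (4.3). Alpha 0.05, sidedness not stated (9.4.3). An annual incidence of 5%, which is a national figure for rape on college campuses (2.2) and not a rate for perpetration, partner violence or all SES items.

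**Assumptions.** Constant hazard; MKit halves new events; the same pre-baseline risk in both arms; two-sided test; 80% power; individual-level comparison with no design effect.

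**Step 1, new-event risk.** With annual rate a, the risk over m months is r(m) = 1 − (1 − a)^(m/12). For a = 0.05:
- r(1) = 0.43%
- r(5) = 2.11%
- r(7) = 2.95%
- r(12) = 5.00%

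**Step 2, a 12-month frame at month 5.** Seven of the 12 recall months precede baseline. The reported proportion is 1 − (1 − r(7))(1 − new-event risk).
- Control: 1 − 0.9705 × 0.9789 = 5.00%
- MKit: 1 − 0.9705 × 0.9894 = 3.97%
- Apparent ratio: 3.97/5.00 = 0.79, against a true 0.50
- Apparent difference: 1.03 points, against a true 2.11/2 = 1.06 points

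The difference is multiplied by 1 − r(7) = (1 − a)^(7/12). That factor is 0.971, 0.940 and 0.878 at assumed annual rates of 5%, 10% and 20%, so the difference is about 3%, 6% and 12% smaller. Its sign does not change.

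**Step 3, other frames.** The direction of the error depends on the frame.

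| Assumed frame | Reported by controls | Relative to 5-month risk (2.11%) | Relative to 1-month risk (0.43%) |
|---|---|---|---|
| 3 months | 1.27% | 0.6 | 3.0 |
| 6 months | 2.53% | 1.2 | 5.9 |
| 12 months | 5.00% | 2.4 | 11.7 |

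With an 'ever' frame and an assumed prior prevalence of 10% to 30%, controls would report 11.9% to 31.5% at 5 months and the ratio would appear as 0.92 to 0.98.

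**Step 4, effect on a later trial.** Per arm, n = [1.96√(2p̄(1 − p̄)) + 0.8416√(p1(1 − p1) + p2(1 − p2))]² / (p1 − p2)², where p̄ is the mean of p1 and p2.
- Correct new-event inputs, 2.11% against 1.06%: (0.3463 + 0.1486)² / 0.010573² gives 2,191.
- 5.0% misread as the new-event rate, 5.0% against 2.5%: (0.5266 + 0.2256)² / 0.025² gives 906.
- Power of 906 per arm at the true risks: Φ[(0.010573 − 1.96 × 0.005870)/0.005864] = Φ(−0.16), about 44%.
- A trial that keeps the 12-month frame, 5.00% against 3.97%: 6,389. This is the cost of the longer frame, not a sizing error.

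**Step 5, precision after the fix.** The expected number of new events among 150 controls is 150 × 0.0211 = 3.2. An assumed 3/150 gives 2.0%, exact 95% CI 0.4% to 5.7%. For a halving, those limits correspond to 11,329 and 785 per arm.

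**The case against.** The strongest objection is that recall frames live in questionnaire stems, and the questionnaires are not in the documents. Saying that the measures are repeated identifies the instruments; it does not prove that the stems were unchanged. This stands. A reader might infer that the surveys definitely collect lifetime or 12-month events. The documents do not support that, and a short frame would err the other way at 5 months (Step 3). What remains is that the plan sets no frame, and that its own description, taken literally, is open-ended.

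Second, the documents never name a new-event rate. They ask for the direction of effects and for data to support power calculations, and direction survives. This also stands: it would be wrong to say that the stated analysis fails. But a power calculation for an event outcome needs an event proportion that belongs to a defined window, and the plan does not supply one.

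Third, the sizing error arises only if a later trial counts new events and takes its rate from a differently framed item. True, and a trial keeping the same frame would be sized correctly, at a larger number.

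Fourth, the corrected rate is so imprecise that the mistaken 906 lies inside the range it implies. That is correct, and it limits the gain. An imprecise estimate of the right quantity, shown with its interval, is still more useful than a proportion whose window is unknown.

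Fifth, changing the stem gives up a like-for-like comparison with baseline in a before-and-after design. That is a real cost, but a raw change in an open-ended past-experience score says little about events after access.

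**Conclusion.** The point holds in limited form. Sections 4.1 and 8.1 repeat past-experience items at follow-up with no look-back, and Section 9.4.3 defines no new-event outcome. Read literally, this mixes events from before MKit access into the follow-up scores, dilutes the contrast between arms, and yields a proportion that does not match the five-month window. A frame longer than the time since baseline overstates new-event risk; a shorter one misses events.

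The figures in the brief rest on an assumed 12-month frame, a constant hazard, an assumed halving, and a background rape incidence that is narrower than these item sets. They show how large the problem could be, not what the surveys will produce.

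Severity is minor. Direction is preserved if pre-baseline risk is alike in the two arms, the absolute difference shrinks only slightly on a 12-month frame, and the primary endpoints are unaffected. The outcomes are secondary and the plan says openly that they are unpowered. A reader might go further and conclude that the pilot's own sample size or its planned direction-of-effect analysis is invalid; nothing in the documents supports that.

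**What to change.** In Sections 4.1 and 8.1, state that at 1 and 5 months the SES victimization, SES perpetration and partner-violence items ask about events 'since your last survey'. Keep the baseline responses, with their own stated look-back, as a baseline variable.

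In Section 9.4.3, add for each of the three item sets the proportion with any new event from baseline to 5 months, by arm with exact confidence intervals, as the summary for power calculations. Count an event reported at either follow-up. A student who missed the 1-month survey has baseline as the last survey, so the 5-month answer still covers the whole interval. Report separately the students with a month-1 event who miss month 5, and those who skip the items (as Section 7.1 allows), so that neither group is silently dropped. The ANOVA of the knowledge, self-efficacy and attitude scores need not change.

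The cost is stem wording in two surveys and one paragraph of analysis text. The Statement of Compliance requires IRB approval before a change is implemented, so approval is needed before the follow-up surveys go out. Raw before/after change will no longer be comparable for these items, and the wording may depart from the cited instruments. The event rate will stay imprecise, so the power calculation should show the range of sizes that its interval implies.
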